7.2.2 Secondary Efficacy Variables

- Change from baseline in the frequency of headache days per 28-day period. This variable will be derived from the daily e-diary reports. It will be based on the count of days with at least 4 continuous hours in total duration of headaches, and/or headache of any duration with the use of migraine-specific acute headache medication(s).
- Change from baseline in total HIT-6 score per 28-day period
- Proportion of patients with a $\geq 70\%$ decrease from baseline in the frequency of headache days per 28-day period. This responder variable will be derived from the underlying primary variable of headache days.

[Redacted]

7.2.3.1 Imputation for Missing Values and Scoring Algorithms

For validated questionnaires, scoring will follow the guidelines set forth by the instrument developers and missing data handled per developer instructions. Imputation methods for missing values and scoring algorithms for other outcome measures will be detailed in the SAP.

Over the course of active treatment, each patient receiving topiramate will record the total daily dose taken in the e-diary system. If a patient skips a dose(s) or fails to take the specific maintenance dosing regimen, the patient will still be able to continue in the study.

Topiramate dosing compliance will be calculated based on the e-dairy data and if necessary, corresponding pill counts (number of pills actually taken, number of pills retrieved/returned, and the number of pills expected to have been taken by the patient while in the topiramate arm of the study). Topiramate dosing compliance details will be provided in the SAP. If the patient indicates that no topiramate treatment was taken in the e-dairy system and treatment discontinuation is reported at the subsequent office visit, then date of last dose taken will be the reported as date of discontinuation.

7.3 Hypothesis and Methods of Analysis

7.3.1 Primary Efficacy Analyses

The primary efficacy analysis is based on the proportion of responders (patients with a $\geq 50\%$ decrease from baseline in the frequency of headache days per 28-day period), and the primary timepoint is defined as the 28-day diary period ending with week 32 (ie, weeks 29 to 32). The primary null hypothesis is that BOTOX and topiramate are equally effective, as measured by the proportion of patients with a $\geq 50\%$ decrease from baseline in the frequency of headache days per 28-day period at week 32. The alternative hypothesis is that BOTOX has a different effect than topiramate.

The primary comparison between treatment groups will be performed using a simple logistic regression model, adjusted by the baseline number of headache days as a covariate. Missing values will be estimated according to the imputation method provided in the SAP. All centers will be pooled for this analysis. A two-sided test with p-value less than or equal to 0.05 will be considered as statistically significant, with the exception that treatment-by-subgroup interactions will be examined at the 0.10 level. If there are convergence issues with the simple logistic regression due to small cell counts, the same logistic regression model will be implemented using exact (conditional) logistic regression analysis.

7.3.2 Secondary Efficacy Analyses

A sensitivity analyses of the primary variable will be performed using (1) Fisher's exact test based on the imputation method discussed in the SAP, and (2) using a similar logistic regression analysis but applying another imputation scheme (to be discussed in the SAP) to impute for missing values when there are less than 20 days of reported data in the e-diary. Other sensitivity analyses will be described in the SAP.

The 3 secondary efficacy variables (Section 7.2.2) are ranked in a hierarchical order of clinical importance. To control for Type I error rate for multiple secondary endpoints, a hierarchical testing gatekeeping procedure will be used, starting with the first secondary endpoint in the ranking order, followed by the next, and so on, in a sequential fashion. If the test of the first secondary endpoint shows statistical significance at the 0.05 level (2-sided), then there is justification to proceed to test the next endpoint in the ranking order; this stepwise process continues for all the endpoints listed in the hierarchical order. However, if no statistical significance is shown at the 0.05 level (2-sided) for the test of any specified endpoint in the hierarchical order, then that endpoint and all subsequent endpoints below this in the ranking order should not be considered statistically significant, regardless of their nominal p-value.

The change from baseline in frequency of headache days will be compared between BOTOX and topiramate groups via analysis of covariance (ANCOVA) with baseline headache day count as the covariate. A treatment-by-investigator site interaction will also be investigated in a separate ANCOVA model.

The HIT-6 score will be compared between treatment groups using a nonparametric rank analysis of covariance (rank ANCOVA) (Stokes et al, 2000), with treatment as a factor, and adjusting for the baseline value.

The $\geq 70\%$ responder rate will be analyzed similar to the primary endpoint, using a logistic regression model adjusted by the baseline frequency of headache days. The exact conditional logistic regression analysis will be performed if there are convergence issues with the default unconditional analysis.

[REDACTED]

[REDACTED]

[REDACTED]

[REDACTED]

[REDACTED]

[REDACTED]

[REDACTED]

7.4 Subgroup Analyses

Subgroup analyses of efficacy and/or safety variables will be detailed in the SAP.

7.5 Sample Size Calculation

Approximately 400 patients (200 per group) are required to provide 90% statistical power to detect an expected treatment difference of 16%. This calculation assumes a topiramate responder rate of 28% and a BOTOX responder rate of 44% at the primary timepoint of week 32. A responder is defined as having a $\geq 50\%$ decrease from baseline in the frequency of headache days per 28-day period. The above calculations were based on a two-sided test at $\alpha = 0.05$, using the commercial software nQuery Advisor version 6.01 (Elashoff, 2005), procedure PTT1 for a two-group continuity corrected Chi-squared test of equal proportions, with equal sample sizes.

The assumed responder rates for BOTOX were estimated from 2 Allergan phase 3 double-blind placebo-controlled studies which reported the observed rates as 43.5% (113/260), 50.5% (141/279), and 47.1% (254/539) for study 191622-079, study 191622-080, and the pooled/combined data, respectively, at the primary timepoint of week 24 (Aurora et al, 2010;

[Diener et al, 2010](#)). At week 32, the observed rates were 55.7% (141/253), 61.7% (161/261), and 58.8% (302/514), respectively, for these studies. The corresponding rates for an ITT analysis where patients terminating the study are treated as failures are obtained as 41.3% (141/341), 46.4% (161/347), and 43.9% (302/688), respectively. Based on these studies, the BOTOX responder rate for an ITT analysis at week 32 ranges from 41.3% to 46.4%, and the value of 44% was chosen as reasonable for the purposes of sample size calculation for the current study.

The topiramate responder rate was estimated from 2 published articles. A double-blind placebo-controlled study with combination therapies, topiramate + placebo (n = 95) and topiramate + propranolol (n = 96) is described in [Silberstein et al, 2012](#). The observed responder rates for $\geq 50\%$ decrease in headache days from baseline reported at week 24 were 28% (23/82) and 31% (26/84), respectively, for the 2 groups. These correspond to 24% and 27%, respectively, for an ITT analysis where patients terminating the study are treated as failures. [Rothrock et al, 2005](#) also describes an open-label study involving topiramate (n = 170), where a responder rate ($\geq 50\%$ reduction from baseline) of 38.8% (45/116) was reported. This rate also corresponds to 29.4% for an ITT analysis where patients terminating the study are treated as failures. Thus, the ITT rates for topiramate ranges from 24% to 29.4%, and the value of 28% is deemed reasonable for sample size calculation purposes.

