The topiramate responder rate was estimated from 2 published articles. A double-blind, placebo-controlled study with combination therapies, topiramate + placebo (n = 95) and topiramate + propranolol (n = 96) is described in Silberstein et al, 2012. The observed responder rates for  $\geq 50\%$  decrease in headache days from baseline reported at Week 24 were 28% (23/82) and 31% (26/84), respectively, for the 2 treatment groups. These rates correspond to 24% and 27%, respectively, for an ITT analysis where patients who terminate from the study are treated as failures. Rothrock et al, 2005 also describes an open-label study involving topiramate (n = 170), where a responder rate ( $\geq 50\%$  reduction from baseline) of 38.8% (45/116) was reported. This rate corresponds to 29.4% for an ITT analysis where patients who terminate from the study are treated as failures. Thus, the ITT responder rate for topiramate ranged from 24% to 29.4%, and the value of 28% was deemed reasonable for sample size calculation purposes.

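### Does the topiramate planning rate of 28% fail because one literature figure, 29.4%, does not follow from the counts printed beside it?

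*Protocol*

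**What the plan says.** Protocol 7.5 sets the planning values: "This calculation assumes a topiramate responder rate of 28% and a BOTOX responder rate of 44% at the primary timepoint of week 32". With a two-sided 5% continuity-corrected chi-squared test, this leads to 200 patients per group for 90% power.

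The BOTOX value rests on two phase 3 studies with Week 32 data: "At week 32, the observed rates were 55.7% (141/253), 61.7% (161/261), and 58.8% (302/514), respectively". With all patients in the denominator, the rates are 41.3% (141/341), 46.4% (161/347) and 43.9% (302/688).

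The topiramate value rests on two publications. For the combination-therapy study (groups of 95 and 96), the rates of at least 50% "decrease in headache days from baseline reported at week 24 were 28% (23/82) and 31% (26/84), respectively"; the protocol converts these to 24% and 27% on an ITT basis. The second publication "also describes an open-label study involving topiramate (n = 170), where a responder rate" "of 38.8% (45/116) was reported", followed by: "This rate also corresponds to 29.4% for an ITT analysis where patients terminating the study are treated as failures". No timepoint is given for this study.

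The protocol concludes that "the ITT rates for topiramate ranges from 24% to 29.4%, and the value of 28% is deemed reasonable". SAP 4.1 carries the same figures: "This rate corresponds to 29.4% for an ITT analysis where patients who terminate from the study are treated as failures".

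**The concern.** A reader who divides 45 by 170 gets 26.5%, not 29.4%. The figure matters to the stated reasoning because 29.4% is the only topiramate ITT rate in the section that reaches 28%. Without it, the ITT range would stop at about 27%, and the planning value would lie above the range it is said to fall within. The two possible corrections also point in opposite directions: a lower true figure makes 28% cautious, while a higher one puts 28% below the top of the published evidence.

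The timepoint raises a second doubt. Both planning rates carry the Week 32 label, yet only the BOTOX evidence is shown at Week 32. One topiramate source is dated Week 24 and the other is undated. The pooled observed BOTOX rate rises from 47.1% at Week 24 to 58.8% at Week 32, so it is fair to ask whether topiramate was assumed flat over the same weeks. If topiramate response were materially higher at Week 32 than assumed, the 16-point difference and the 90% power would be optimistic.

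**Working it through.** **Inputs** (Protocol 7.5, repeated in SAP 4.1): rates 28% and 44%; two-sided alpha 0.05; power 90%; equal groups; continuity-corrected chi-squared test; the literature counts listed below.

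**Step 1. Reproduce the plan's sample size.** With p1 = 0.28, p2 = 0.44, mean rate 0.36 and d = 0.16:

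- Uncorrected n per group = [1.960 × √(2 × 0.36 × 0.64) + 1.2816 × √(0.28 × 0.72 + 0.44 × 0.56)]² / 0.16² = (1.3305 + 0.8578)² / 0.0256 = 187.0.
- Corrected n = (187.0/4) × [1 + √(1 + 4/(187.0 × 0.16))]² = 199.4, rounded up to 200.
- Corrected power at 200 per group: 90.1%.

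The stated N and power follow from the stated rates.

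**Step 2. Recompute each ITT rate as responders divided by all patients.**

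| Source | Counts | Computed | Printed |
|---|---|---|---|
| BOTOX, study 079, Week 32 | 141/341 | 41.3% | 41.3% |
| BOTOX, study 080, Week 32 | 161/347 | 46.4% | 46.4% |
| BOTOX, pooled, Week 32 | 302/688 | 43.9% | 43.9% |
| Topiramate + placebo, Week 24 | 23/95 | 24.2% | 24% |
| Topiramate + propranolol, Week 24 | 26/96 | 27.1% | 27% |
| Topiramate, open-label, undated | 45/170 | 26.5% | 29.4% |

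Five of six agree. The observed rate for the sixth study is right: 45/116 = 38.8%. A value of 29.4% needs either 50/170 = 29.4% or 45/153 = 29.4%. Neither 50 nor 153 is printed.

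**Step 3. Consequence for power.** Hold BOTOX at 44% and 200 per group. The continuity correction is equivalent to working with an uncorrected n of 200 − 2/d + 1/(200d²); for d = 0.16 this is 200 − 12.5 + 0.2 = 187.7.

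| Topiramate rate | Where it comes from | Power |
|---|---|---|
| 24.2% | 23/95 | 98.4% |
| 26.5% | 45/170 | 94.9% |
| 27.1% | 26/96 | 93.2% |
| 28.0% | planning value | 90.1% |
| 29.4% | printed upper end | 83.6% |
| 30.0% | rate at which power reaches 80% | 80.1% |

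Every topiramate ITT rate in the documents, on either reading of the open-label study, leaves power above 80%.

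**Step 4. Timepoint.** The rise from 47.1% (254/539) to 58.8% (302/514) is in observed cases, and the denominator shrinks by 25. The planning values are ITT rates, so this rise cannot be transferred to them directly. For topiramate there is also a force in the other direction: Protocol 6.1.1 and SAP 8.1.1 count patients who stop topiramate and move to BOTOX as nonresponders. Any such discontinuation between Weeks 24 and 32 lowers the topiramate ITT rate. The documents do not show the net direction.

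**The case for a change.** The strongest case for a change is that a figure disproved by one division is the only support for saying that 28% lies inside the published ITT range. It appears in both documents and could be carried into the study report. The correction would cost a few words. The Week 32 label on the topiramate rate has no Week 32 source behind it, and power against 44% drops below 80% once topiramate exceeds about 30.0%, only two points above the assumption.

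Part of this stands. The 29.4% does not follow from 45 and 170, its denominator is not printed, the open-label study has no date, and no Week 32 topiramate rate is cited.

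The rest does not carry to a change. A misprinted count is not established: 45, 116, 170 and 29.4% could all be correct if the ITT denominator were 153, and the protocol gives 170 as the study's n without calling it the ITT denominator. The statement that 29.4% alone reaches 28% is true only of ITT rates; the observed rates in the same paragraph are 28%, 31% and 38.8%. The Week 24 date of the combination study is disclosed, and borrowing a rate from a nearby week for a planning assumption is ordinary practice. The 30.0% threshold lies above every topiramate ITT rate printed.

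**Conclusion.** The discrepancy is real, but it is a traceability slip in the literature background to a planning assumption. The figure 29.4% enters no formula. The calculation uses 28% and 44%, and it reproduces: 200 per group, 90.1% power.

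Both readings leave the design where it is. If 45/170 is right, the topiramate ITT range is 24.2% to 27.1%, and 28% is slightly conservative, with 94.9% power at 26.5%. If 29.4% is right, 28% sits inside the range as stated, and 83.6% is the power at its upper end. The documents alone cannot decide between them, and nothing in the trial depends on the answer.

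The timepoint gap is a fair limitation of the evidence available for planning, and the text presents 28% as an assumed, reasonable value. It does not show that the trial is underpowered.

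These power figures assume a BOTOX rate of 44%, 200 analysed per group and the plan's continuity-corrected test. The 28%, the 44%, the 90% power, the 400 patients, the endpoint, the analysis and the conclusions all stay as they are.

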7.6 Interim Analysis

No interim analysis is planned for this study.

8. Study Visit Schedule and Procedures

Please see Table 1 for a schematic of the schedule of visits and procedures.

8.1 Patient Entry Procedures

8.1.1 Overview of Entry Procedures

Prospective patients as defined by the criteria in Sections 4.3 and 4.4 (inclusion/exclusion criteria) will be considered for entry into this study.

8.1.2 Informed Consent and Patient Privacy

The study will be discussed with the patient and a patient wishing to participate must give informed consent prior to any study-related procedures or change in treatment. The patient must also give authorization and other written documentation in accordance with the relevant country and local privacy requirements (where applicable) prior to any study-related

8.5 Instructions for the Patients

At approximately the same time (preferably at the beginning and end of the day) on a daily basis during the 28-day run-in period and throughout the study duration, patients are to report information, using an e-diary, on the total duration of all headaches (in hours), maximum severity of headaches that occurred that day (as mild, moderate or severe), any acute headache pain medication(s) used that day, and for those patients taking topiramate, the dose of topiramate that day. Patients will be able to report headache data, including absence of headache, for the day of the e-diary report and for the previous day(s). Patients will be asked to complete the MIBS-4 questionnaire only on the specific day(s) when a duration of 0 headache hours are reported in the e-diary.

Patient-reported outcome questionnaires (ie, HIT-6, ACM-I, PHQ-9, COWAT, WPAI-SHP, and PTS) are to be completed by the patient via the eCOA on days specified in the visit schedule (Table 1), and the answers to the questions on the questionnaires should come from the patients directly, not from family, friends, or the study support personnel. Patient instructions and training for completing the e-diary and eCOA will be provided to the site.

Patients receiving topiramate will be instructed on the daily dosing schedule. At the day 1 office visit, patients will receive an initial topiramate dose of 25 mg/day and will be instructed to continue this dose for 1 week. Patients will be instructed that, during the next 3 weeks, the topiramate dose should be increased in weekly increments of 25 mg/day until a dose of 100 mg/day (or a lower maximum tolerated dose) is reached. Upon discussion with the investigator, the patient may also decrease the dose until the topiramate dose is optimized. At the next scheduled office visit (ie, week 12), the investigator may adjust the topiramate dose (upward or downward) at his/her discretion and the patient will be instructed to remain on this dose for the remainder of topiramate treatment in the study. Patients should report in the daily e-diary the doses of topiramate taken each day. Patients should consult with the investigator regarding any changes made to their instructed topiramate dosing schedule. If the patient decides to stop taking topiramate, for any reason, they should contact their investigator to ensure an appropriate tapering regimen and unused pills should be returned at next visit. The patient should continue to complete their daily diary and the treatment discontinuation eCRF can be completed at the subsequent office visit. The patient treatment discontinuation eCRF must be completed to determine reason for discontinuation.

Patients may use medication(s) with a known headache prophylactic effect and take prescription or OTC acute headache pain medications, as prescribed and/or directed by the investigator. Any medication with a known headache prophylactic effect used by the patient should be maintained at a stable dose and dosage regimen during the study. Patients should

not receive acupuncture, TENS, cranial traction, dental splints for headache, or injection of steroid or anesthetics into the study target muscles at any time during the study. Patients should be advised of the use of medications that may interact with topiramate during the study (see Section 4.5.2).

Females of childbearing potential will be counseled on using reliable methods of contraception during the study. The investigator and each patient will determine the appropriate methods of contraception for the patient and/or partner (see Section 4.5.1.1).

Throughout the study, patients should maintain the same or similar level of caffeine ingestion.

8.6 Unscheduled Visits

All procedures and evaluations necessary for the well-being of the patient should be performed, if necessary at an unscheduled visit, and eCRFs should be completed if appropriate.

8.7 Compliance with Protocol

Patients will be scheduled for follow-up visits in a timely manner and these should occur as close as possible to the day specified in the visit schedule (Table 1). At each visit, the patient will be asked if the patient changed the dose/regimen of any existing concomitant medications, initiated the use of any new concomitant medications, or had any concurrent procedures since the last visit to ensure compliance with the protocol. Both BOTOX and topiramate study treatments should be administered per protocol. Given topiramate is self-administered, patients will also record in the daily e-diary if the topiramate treatment was taken and the specific dose each day to ensure compliance with titration and maintenance dosing. If the specified dose is not recorded, the patient will be able to continue in the study and criteria for adequate topiramate compliance will be detailed in the SAP.

8.8 Early Discontinuation of Patients

Patients may voluntarily withdraw consent from the study at any time. If the patient withdraws consent due to any reasons other than treatment discontinuation (eg, patient moved, patient does not complete visits), all of the final measurements should be performed at the exit visit and recorded on the appropriate eCRF. The eCRF for patient treatment discontinuation should be completed to document patient withdrawal of consent.

If a patient discontinues topiramate treatment, the eCRF for patient treatment discontinuation should be completed to document the reason for discontinuation. The patient should not be

exited from the study, but should be administered BOTOX at the next scheduled office visit (ie, week 12, 24, or 36).

If a patient discontinues BOTOX treatment, the eCRF for patient treatment discontinuation should be completed to document the reason for discontinuation. The patient should then be exited from the study and all of the final measurements should be performed at the exit visit and recorded on the appropriate eCRFs.

If a patient is determined as a loss to follow-up, the eCRF for patient treatment discontinuation should be completed to document the reason for discontinuation.

If a patient must exit the study due to pregnancy or the C-SSRS (ie, the patient answers “yes” to questions 4 or 5 in the suicidal ideation section or “yes” to any question in the suicidal behavior section), the eCRF for patient treatment discontinuation should be completed to document the reason for discontinuation. The patient should then be exited from the study and all of the final measurements should be performed at the exit visit and recorded on the appropriate eCRF.

Notification of early patient discontinuation from the study and the reason for discontinuation will be made to Allergan or Allergan designee and will be clearly documented on the appropriate eCRF.

